## 4.8. Data analysis:

Data will be analyzed using SPSS software version 21. Baseline patient characteristics will be described using descriptive statistics. Continuous variables will be expressed using mean and standard deviation or median with range depending on the distribution of data. Categorical variables will be expressed using frequency and percentage. Primary analysis will be done using a modified intention to treat (mITT) analysis where only subjects with at least one follows up assessment done will be included in the analysis.

Mean change in CAP score and LSM from baseline to 6 months will be compared between the 2 groups (Caffeine tablets vs placebo) using Independent T test or Mann Whitney U test depending on the distribution of data. For the secondary endpoints continuous variables will be compared using Independent T test or Mann Whitney U test and categorical variables will be compared using Chi square test. Repeated measures ANOVA will be used for analysis of change in variables from baseline till end of study. P value less than 0.05 will be considered statistically significant.

Safety outcomes will be described using descriptive statistics. For patients who were lost to follow up, the last available value will be used for analysis.

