#### 5.5. Follow up assessment

The recruited patients will be advised to come for monthly assessments and will be asked to attend the nearest hospital, if they develop any complications and inform the study team of such incidence.

The degree of adherence to prescribed lifestyle changes and diet will be recorded at the baseline and monthly follow-up visits. Physical activity and alcohol consumption will also be monitored at the baseline and monthly follow-up visits.

Anthropometric measurements, physical examination and vital sign measurements (BP, HR, RR etc..) will be monitored at the baseline and each monthly visit. Details on concomitant medications will be recorded in monthly visits.

Liver profile, Lipid profile, Full blood count, Serum creatinine, fasting blood glucose, HbA1c, serum insulin, serum electrolytes and urine analysis and serum insulin will be investigated at the baseline, at 3 months and 6 months.

Fibro scan will be done at the baseline and after 6 months at the completion of the study.

The details of items which will be measured on every visit are described in Table 2.

Table 2: Summary of follow up

	Enrolment	Allocation 1	Subsequent visits							
TIME POINT		0	1 st	2 nd	3 rd	4 th	5 th	6 th		
			mont	mont	month	mont	month	mont		
			h	h		h		h		
ENROLMENT										
Eligibility screen	×									
Informed consent	×									
Allocation		×								
INTERVENTIO										
NS										
caffeine or		×	×	×	×	×	×			
placebo										
ASSESSMENTS										
Medical history	×	×	×	×	×	×	×	×		
taking										
AUDIT	×	×	×	×	×	×	×	×		
FFQ and IPAQ	×	×	×	×	×	×	×	×		

Height, weight			×	×	×	×	×	×
and waist								
circumference								
Blood pressure	×	×	×	×	×	×	×	×
Physical examination 	×	×	×	×	×	×	×	×
USS scan	×							
Fibro scan		×						×
FBG	×	×			×			×
Fasting serum insulin		×			×			×
HCG only female	×							
Serum HbA1c		×			×			×
Lipid profile	×	×			×			×
Liver enzymes	×	×			×			×
Total bilirubin	×				×			×
Serum creatinine		×			×			×
Serum electrolytes		×			×			×

FBC	×		×		×
UFR	×		×		×

28.02.2025

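### The added repeated measures ANOVA drops anyone who misses an interim visit, because Section 4.8 fills values only for patients lost to follow-up

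*Protocol*

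**What the plan says.** Section 4.8 of the protocol makes these choices:

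- **Software:** "Data will be analyzed using SPSS software version 21".
- **Population:** "Primary analysis will be done using a modified intention to treat (mITT) analysis where only subjects with at least one follows up assessment done" are included. The sentence concerns the primary analysis.
- **CAP and LSM:** the mean six-month change in each "will be compared between the 2 groups (Caffeine tablets vs placebo) using Independent T test or Mann Whitney U test depending on the distribution".
- **Secondary endpoints:** "For the secondary endpoints continuous variables will be compared using Independent T test or Mann Whitney U test".
- **Further analysis:** "Repeated measures ANOVA will be used for analysis of change in variables from baseline till end of study". Neither the variables nor the time points are named.
- **Missing values:** "For patients who were lost to follow up, the last available value will be used for analysis". Nothing is said about a visit missed by someone who stays in the trial.

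The measurement schedule is in Section 5.5 and Table 2. Anthropometry "will be monitored at the baseline and each monthly visit", which makes six follow-up values. Laboratory tests are done at baseline, 3 months and 6 months. The FibroScan is done at baseline and 6 months only. Section 2.4 lists waist, weight, BMI and the liver enzymes as secondary endpoints, each from baseline to week 24.

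**The concern.** Classical repeated measures ANOVA needs a complete profile: one gap removes the whole participant. Carrying the last value forward completes the profiles of patients who are lost after at least one follow-up visit. It does not, as worded, reach someone who misses month 2 and returns for months 3 to 6, because that person is not lost.

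The same secondary endpoint would then be analysed on two sets of people. The t test or Mann-Whitney test needs only baseline and month 6 and keeps this participant. The ANOVA removes them, although their month-6 value was observed. The ANOVA set can thus be smaller than, and different in kind from, the set with at least one follow-up, since it favours regular attenders. Section 6.1 expects palpitations, insomnia and gastrointestinal discomfort on caffeine. If such effects influence attendance, the selection could differ by arm.

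**Working it through.** **Inputs from the protocol**

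- 55 participants per group (Section 4.4). The figure reproduces with the standard two-sample formula: 2 × 5² × (1.96 + 0.84)² / 3² = 43.6, so 44 per group, and 44 / 0.80 = 55 after 20% dropout.
- Weight, waist and BMI: six follow-up visits, of which five (months 1 to 5) are interim.
- Laboratory endpoints: two follow-up visits, of which one (month 3) is interim.
- FibroScan: one follow-up visit, none interim.

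**Assumptions, not in the protocol**

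- Each interim visit is missed with probability m, independently of the others; m = 2%, 5% or 10%.
- Every scheduled value enters the ANOVA, and a single missed value is not filled.

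**Formula.** The participants of interest attended month 6. With k interim visits, the share of them that the ANOVA drops is 1 − (1 − m)^k. The standard error is multiplied by √(1 / (1 − m)^k), whatever the starting number. The counts below start from 55 per arm, as if all had an observed month-6 value.

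| Endpoint | k | m | Share dropped | Left of 55 | Standard error × |
|---|---|---|---|---|---|
| Weight, waist, BMI | 5 | 2% | 1 − 0.98^5 = 9.6% | 49.7 | 1.05 |
| | 5 | 5% | 1 − 0.95^5 = 22.6% | 42.6 | 1.14 |
| | 5 | 10% | 1 − 0.90^5 = 41.0% | 32.5 | 1.30 |
| Laboratory values | 1 | 2% | 2% | 53.9 | 1.01 |
| | 1 | 5% | 5% | 52.3 | 1.03 |
| | 1 | 10% | 10% | 49.5 | 1.05 |
| CAP, LSM | 0 | any | 0% | 55 | 1.00 |

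**How far the reading of the text matters.** If the ANOVA for weight used only months 0, 3 and 6, the loss at m = 5% would be 5%. If it used only months 0 and 6, or if the last-value rule were also applied to single missed visits, the loss would be 0%. Section 4.8 does not say which applies.

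**The case against.** The strongest reply is that no named endpoint comparison is harmed. CAP, LSM and the continuous secondary endpoints each have a two-group test that ignores interim visits, and the ANOVA is an addition. This stands, and it confines the point to the ANOVA.

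It also rules out several stronger readings that a reader might infer:

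- *The ANOVA contradicts the mITT population.* The mITT sentence governs the primary analysis, and CAP and LSM are not assigned to the ANOVA. The protocol is silent on incomplete profiles in the ANOVA; it does not contradict itself.
- *Observed month-6 values are lost to the trial.* They are lost only from the ANOVA.
- *The loss at 5% is 26.5% for monthly variables and 9.8% for laboratory values.* These are 1 − 0.95^6 and 1 − 0.95^2. They also count people who miss month 6 itself and so have no observed endpoint to discard.
- *A primary endpoint is at risk through FIB-4.* Section 4.8 names no test for FIB-4, but it does not assign it to the ANOVA either, so the text does not settle this.

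A further reply is that handling of gaps belongs in a statistical analysis plan, which may exist. That would answer a mere omission. Here the protocol itself fixes both a method that deletes incomplete profiles and a filling rule limited to patients lost to follow-up.

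Finally, missed visits may cluster in the same people. For a given overall miss rate, fewer participants would then be affected than the independence figures suggest.

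**Conclusion.** The point holds for the repeated measures ANOVA alone. As written, that analysis removes participants who miss an interim visit but attend month 6, so its set can fall below those with at least one follow-up and can differ from the set used for the same secondary endpoint elsewhere in Section 4.8.

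For weight, waist and BMI the loss is about 10%, 23% or 41% of participants with an observed month-6 value at assumed miss rates of 2%, 5% or 10%. For laboratory endpoints it is 2%, 5% or 10%. At 5%, about 43 of 55 per arm remain for the monthly variables, with a standard error about 14% larger. These sizes rest on independent misses, on all scheduled values entering the model and on no filling of single gaps. A difference in attendance between arms is possible, but the protocol gives no figure for it.

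**What to change.** In Section 4.8, replace repeated measures ANOVA with a linear mixed model on all observed follow-up values, with arm, visit, arm-by-visit interaction and baseline as terms and an unstructured covariance. Name the variables it covers and the visits that enter for each. Report the month-6 difference between arms with its 95% confidence interval.

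Every participant with a baseline and at least one follow-up value of the variable then stays in, and no interim gap needs filling. SPSS offers the model, so software, visits and data collection do not change. The cost is a sentence or two in the protocol and slightly more analysis work. It is best done before the data are analysed, because the protocol requires ethics committee approval for later departures from the statistical plan.

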## 2. Hypothesis, Objectives, Outcomes and End points

## 2.1. Hypothesis:

- **Null Hypothesis**: Coffee (caffeine) supplementation has no effect on hepatic steatosis and fibrosis in NAFLD patients.
- Alternative Hypothesis: Coffee (caffeine) supplementation reduces hepatic steatosis and fibrosis in NAFLD patients.

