#### Secondary Outcome

The secondary outcome is to compare the reduction of AST and ALT levels

28.02.2025

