#### 2.4. End Points:

#### **Primary endpoints**

- 1. Reduction in Liver stiffness measurement (LSM) as determined by fibroscan of liver from baseline to week 24.
- 2. Reduction in Hepatic steatosis with controlled attenuation parameter (CAP) as determined by fibroscan from baseline to week 24.
- 3. Reduction in Fib-4 score as determined by calculation from baseline to week 24.

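### Three primary endpoints, a named primary test for only two, and no rule for how many must succeed: the stated 5% error and 80% power cannot both describe the trial's conclusion

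*Protocol*

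**What the plan says.** The Protocol's list of primary endpoints (section 2.4) has three numbered items of equal rank. The first is the fall in LSM and the second is the fall in CAP, both measured by Fibroscan over 24 weeks. The third is given as: "Reduction in Fib-4 score as determined by calculation from baseline to week 24". The synopsis, the primary objective (2.2) and the primary outcome (2.3) name the same three measures.

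Section 4.8 then specifies the primary comparison: "Mean change in CAP score and LSM from baseline to 6 months will be compared between the 2 groups", by t test or Mann-Whitney test. It moves straight on to the secondary endpoints and does not mention FIB-4. One threshold covers everything: "P value less than 0.05 will be considered statistically significant". There is no division of alpha, no testing order and no co-primary statement.

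The alternative hypothesis (2.1) reads: "Coffee (caffeine) supplementation reduces hepatic steatosis and fibrosis in NAFLD patients". Nothing turns this into a decision rule.

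Section 4.4 gives one sample-size calculation: two-tailed alpha 0.05, 80% power, SD 5, mean difference 3, 20% dropout, 55 per group. It names neither the endpoint nor the unit.

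**The concern.** With several primary endpoints, the trial's error rate and power depend on the rule that turns the separate results into one conclusion. If one significant result is enough, each extra test adds a chance of a false positive. If every result must be significant, each extra test is another chance to miss. The Protocol gives the ingredients (three endpoints, a test, a threshold) without the rule, and sizes the trial as if there were a single comparison.

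FIB-4 adds to this. It is declared primary but has no named primary test, so even the number of primary tests is unclear. A result with, say, CAP significant and LSM not could be reported as success or as failure, and the choice could be made after the data are seen.

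**Working it through.** **Inputs from the Protocol (4.4):** z for two-sided 0.05 = 1.96; z for 80% power = 0.84; SD 5; difference 3; dropout 20%; 55 per group.

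**Assumptions, because the Protocol gives no figures:** the primary test statistics are jointly normal with a common pairwise correlation r between 0 and 0.8, and each endpoint has 80% power.

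**Step 1. Reproduce the sample size.** The standard two-group formula is n = 2σ²(z₁ + z₂)²/Δ².

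- n = 2 × 25 × (1.96 + 0.84)² / 9 = 2 × 25 × 7.84 / 9 = 43.6, so 44 evaluable per group.
- 44 / 0.8 = 55 randomised per group, 110 in total. This matches the plan.
- Power at 44 per group is 80.4%.

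The formula as it appears in 4.4 lacks the factor 2 and the square on the difference. That may be a typesetting or text-extraction fault and is not pressed here, since the standard formula returns the stated figure. The stated 55 therefore corresponds to **one** comparison at 0.05, with no allowance for several primary endpoints.

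**Step 2. Any one endpoint suffices: familywise error (two-sided).** For k independent tests it is 1 − 0.95^k.

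- Two tests (CAP, LSM): 1 − 0.95² = 0.0975
- Three tests (adding FIB-4): 1 − 0.95³ = 0.1426

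With correlated statistics (multivariate normal):

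| r | two tests | three tests |
|---|---|---|
| 0 | 9.8% | 14.3% |
| 0.5 | 9.1% | 12.5% |
| 0.8 | 7.8% | 9.8% |

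These count a false positive in either direction. Counting only false claims of benefit, at 0.025 per test and independence:

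- two tests: 1 − 0.975² = 4.9%
- three tests: 1 − 0.975³ = 7.3%

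These compare with 2.5% for a single test.

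**Step 3. Any one endpoint suffices: power.** The chance of at least one success when every endpoint has 80% power is, under independence, 1 − 0.2² = 96% for two and 1 − 0.2³ = 99% for three. At r = 0.8 it is about 87% and 90%. Under this rule power is not lost.

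**Step 4. All must succeed.** The error rate stays at or below 5%, because every test has to reject. Joint power under independence is 0.8^k:

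- Two endpoints: 0.8² = 64%, rising to about 73% at r = 0.8
- Three endpoints: 0.8³ = 51%, rising to about 69% at r = 0.8

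**Step 5. Compare.**

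| Rule | Error at 5%? | Power at least 80%? |
|---|---|---|
| Any one suffices | No (7.8–14.3%) | Yes |
| All must succeed | Yes | No (51–73%) |

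Over this range of correlations, neither rule delivers both stated properties.

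**The case against.** **Multiplicity is often left to a SAP.** That is fair in general, and the SAP is not at hand. But section 4.8 does not defer the matter. It fixes the tests and a blanket threshold itself, and the paragraph on deviations treats this as the original statistical plan. Naming a primary endpoint without its primary test is an inconsistency inside the Protocol.

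**The hypothesis already says steatosis and fibrosis, so all must succeed.** This is a reasonable reading, but the text does not make it a decision rule. It also does not say whether fibrosis means LSM, FIB-4 or both.

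**FIB-4 is covered by another sentence.** Section 4.8 adds: "Repeated measures ANOVA will be used for analysis of change in variables from baseline till end of study". This could take in FIB-4, but it neither names it nor marks the analysis as primary.

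**Stronger readings that the documents do not support.**

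- A reader might infer that both the error rate and the power fail whichever rule applies. They do not: each rule breaks one property and keeps the other.
- A reader might take 14.3% as the trial's error rate. That figure needs a FIB-4 test that 4.8 does not name, independence, and counting harm as success. For the two named tests the ceiling is 9.8%.
- A reader might infer that any adjustment would leave the trial badly underpowered. Power for each endpoint does fall, but with alpha split across three, power for at least one success stays at about 79–96% under the assumptions above.
- A reader might infer that the fibrosis endpoints are wrongly ranked because entry requires CAP >263 and sets no minimum LSM or FIB-4. That is a design opinion. The title, objective and hypothesis give fibrosis equal weight.

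**Conclusion.** The point stands. The Protocol declares three primary endpoints, names a primary between-group test for two, applies 0.05 to each, and gives no rule for success, while its sample size fits a single unnamed comparison.

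The consequence depends on the rule that the sponsor intends. Under an any-one rule the two-sided familywise error is 7.8–9.8% for two tests or 9.8–14.3% for three, with power preserved. Under an all-must-succeed rule error is controlled, but joint power is about 64–73% or 51–69%.

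The ranges rest on assumed correlations of 0 to 0.8. The power figures also rest on an assumed 80% power for each endpoint. Section 4.4 ties its SD and difference to no endpoint, so the power figures are illustrative. Their direction does not depend on the exact values. Because the missing rule decides what the trial may conclude, it should be settled before any unblinded data are seen.

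**What to change.** In section 4.8:

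1. Add the between-group comparison for change in FIB-4 from baseline to week 24.
2. State one pre-specified success rule that holds familywise error at 0.05. Workable options are:
   - **Fixed sequence**, for example CAP, then LSM, then FIB-4, each at two-sided 0.05 only if the previous test succeeds. No increase in sample size is needed on multiplicity grounds. The cost is that fibrosis cannot be claimed if CAP fails.
   - **Holm across the three.** Any endpoint can be claimed on its own, at the cost of a stricter first threshold (0.05/3 = 0.0167).
   - **All must succeed, each at 0.05.** This is closest to the hypothesis as worded. The stated power must then be lowered to match. Keeping 80% joint power for three independent endpoints at the planned standardised effect (3/5 = 0.6) would need 0.8^(1/3) = 92.8% power on each, hence 66 evaluable and 66/0.8 = 82.5, so 83 randomised per group (166 in total).

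In section 4.4, state which endpoint, and in what unit, the SD of 5, the difference of 3 and the 80% power refer to.

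The choice among these rules is the sponsor's. Apart from a larger sample under the third option, the cost is Protocol wording only.

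As a separate wording correction with no bearing on primary error or power, align the lower tiers. Section 2.2 has HbA1c and lipids as secondary objectives, and section 2.4 has them as exploratory endpoints. Section 2.3 says only that "The secondary outcome is to compare the reduction of AST and ALT levels", while 2.4 also lists GGT, anthropometric measures and the fatty liver index as secondary.

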## **List of Tables**

Table 1: Summary of Blood Sample Collection

Table 2: Summary of follow up

1.	Title:	Randomized, Quadruple-blind, Placebo-controlled, Clinical Trial to determine the effects of Coffee (caffeine) supplementation on Hepatic Steatosis and Fibrosis in Metabolic dysfunction-associated Steatotic Liver Disease(MASLD)
2.	Objective	
 
Primary Objective:         
 
To assess the effect of coffee (caffeine) supplementation on hepatic steatosis and fibrosis in NAFLD patients measured by CAP score using Fibro scan and Hepatic fibrosis measured by TE using Fibro scan and FIB-4 score
 
 
 
Secondary Objectives:         
 
To assess changes in liver enzymes (ALT, AST, GGT) with caffeine supplementation.
 
To assess the impact on metabolic markers(HbAIC, lipid profile, BMI).
 
To assess potential side effects of caffeine supplementation.
 
 
 

3.	Study design	Randomized, Quadruple blinded, Placebo-controlled
4.	Study setting	Gastroenterology Clinic, University Medical Unit, Colombo North Teaching Hospital, Ragama, Sri Lanka.
5.	Study population	Patients attending the clinic
6.	Definition of intervention/main exposure variable	
7.	Definition of primary outcome	Is the reduction in hepatic steatosis and fibrosis in non-alcoholic fatty liver disease (NAFLD) patients which is measured by Liver stiffness measurement (LSM) via Fibro scan, Controlled attenuation parameter (CAP) scores via Fibro scan and FIB-4 score calculation. All comparisons will be from baseline to week 24.
8.	Sample size	110 participants
9.	Data collection method	It would be conducted by two MBBS-qualified researchers trained in the study protocol.  Interviewer-administered questionnaires will collect demographic and clinical data.  Case Report Forms (CRFs) will document medical history, anthropometric measurements, clinical findings and investigation findings.  Monthly follow-ups will include:  • Physical exams, monitoring of adherence, side effects, and lifestyle factors (diet, exercise, alcohol intake)  In 3 months and 6 months  • Blood investigations, fibro scan and US scan findings
10.	Proposed data analysis	Data will be analyzed using SPSS software version 21

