#### Ultrasound and Fibro scan

At the baseline Ultrasound scan will be performed to confirm the diagnosis of NAFLD.
 After recruitment at the baseline and at the end of six months a fibro scan will be done to assess the efficacy parameters. The ultrasound and fibro scan will be done at North Colombo Teaching hospital

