#### Criteria for stopping the trial or discontinuation of study intervention

28.02.2025

Individual subjects dosing will be stopped immediately if clinically relevant allergic reaction/ hypersensitivity occurs which needs medical intervention.

- 1. Dosing will be stopped if liver enzymes increases > 3 x normal range
- 2. Dosing will be stopped if conjugated bilirubin increases > 1.5 x normal range
- 3. Dosing will be stopped if serum creatinine increases > 1.5 x normal range
- 4. Dosing will be stopped if subjects suffer from a drug related (assessed as possibly or probably) and clinically relevant AE of moderate or severe intensity.
- 5. Any clinically significant values outside the reference ranges with major deviation and/or possible pathological relevance in physical examination, biochemical examination, hematology, vital signs measurements, electrocardiogram (ECG), and urinalysis.
- 6. Patients with AUDIT score > 8.

A volunteer can decide to withdraw from study participation at any time, for any reason, specified or unspecified, and without penalty or loss of benefits to which the subject is otherwise entitled. In this case, the subject must immediately contact the investigator and state that he is leaving the study.

Reasons for the withdrawal of the study (AE, ineffective treatment, inability to comply with the study requirements etc.) will be sought, if the patient is willing to provide that information. They will be made aware that their decision will in no way affect their treatment, and that they will be free to withdraw from study at any time. To respond to questions and record complaints during the study, contact details of two investigators will be provided to the study participants. Patient can be withdrawn from the study upon the principal investigator's decision to terminate the study, based on study compliance and adverse reactions development such as low rates of compliance, complications, or inability to tolerate the medication etc.

28.02.2025

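### For analysed patients lost before month 6, carrying the last value forward sets the change in CAP and LSM to exactly zero, which shrinks a true effect and can bias either way if dropout differs by arm

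*Protocol*

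**What the plan says.** Three statements in the protocol combine.

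- **Missing data.** Section 4.8 says: "For patients who were lost to follow up, the last available value will be used for analysis". No endpoint is exempted.
- **Comparison and analysis set.** Section 4.8 also says: "Mean change in CAP score and LSM from baseline to 6 months will be compared between the 2 groups". The primary analysis is mITT, in which "only subjects with at least one follows up assessment done will be included in the analysis". The kind of assessment is not defined; follow-up visits are monthly.
- **Scan schedule.** Section 5.5 says: "Fibro scan will be done at the baseline and after 6 months at the completion of the study". Section 4.6 agrees ("After recruitment at the baseline and at the end of six months a fibro scan will be done to" assess efficacy), and so does Table 2, which marks Fibroscan at allocation and month 6 only.

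One place conflicts. Item 9 of the synopsis table lists, for months 3 and 6, "Blood investigations, fibro scan and US scan findings".

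The third primary endpoint in section 2.4, "Reduction in Fib-4 score as determined by calculation from baseline to week 24", rests on blood results. Tables 1 and 2 schedule bloods at baseline, month 3 and month 6.

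Section 7.7 lets the principal investigator withdraw a participant from the study "based on study compliance and adverse reactions development such as low rates of compliance, complications, or inability to tolerate the medication etc". It does not say whether such a participant still has the month-6 scan.

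**The concern.** For CAP and LSM under the section 5.5 schedule, the last-value rule amounts to carrying the baseline forward. A patient seen at month 1 and then lost counts as a follow-up case, but the last scan on file is the baseline one. The analysis records no change, although nothing was measured after baseline.

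Zero is not a neutral value here. Section 5.1 gives diet and exercise advice to both arms, and section 5.2 plans a calorie deficit for overweight patients. Some change is therefore plausible even on placebo. Imputed zeros pull each arm's mean towards zero in proportion to that arm's share of zeros. If the shares are equal, a true difference is diluted. If they differ, part of the difference between arms reflects who dropped out rather than what caffeine did. Two of the three primary endpoints are affected.

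**Working it through.** **Inputs from the protocol (section 4.4):** SD 5, expected difference 3, two-sided alpha 0.05, power 80%, dropout 20%, 55 per arm. The SD and difference are not tied to an endpoint or unit.

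**Assumed inputs, not in the protocol:** the mean change in each arm, any dropout rates that differ by arm, and that dropouts' unseen changes resemble those of completers in the same arm.

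**1. The plan's sample size.** The standard two-sample formula gives n = 2 × 5² × (1.96 + 0.84)² / 3² = 43.6, so 44 per arm. Then 44 / 0.8 = 55 per arm, which matches. With 44 completers per arm, power for a difference of 3 is 80.4%.

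**2. Model for the zeros.** In an arm with true mean change m and a share q of analysed patients set to zero:

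- mean = (1 − q) × m
- variance = (1 − q) × (SD² + m²) − mean²

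The difference is caffeine minus placebo, so a negative value favours caffeine.

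**3. Equal dropout, true difference 3.** If all planned dropouts (11 of 55 per arm) enter the mITT set, q = 0.2. The expected difference is 0.8 × 3 = 2.4 in size, whatever the placebo change.

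- Placebo 0, caffeine −3: variances 20.0 and 21.44; SE = √(41.44 / 55) = 0.868; power 79.0%.
- Placebo −3, caffeine −6: SE 0.926; power 73.6%.
- Placebo −6, caffeine −9: SE 1.033; power 64.2%.

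In the first case the shift is 0.6 with SE 0.868, so a 95% interval covers the true 3.0 about 89% of the time.

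**4. Only half of the dropouts enter the mITT set.** q = 0.1 / 0.9 = 0.111, and the difference is 3 × 0.889 = 2.67.

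**5. Equal dropout, no true effect.** Both arm means shrink by the same factor. The difference is 0 and type I error stays at 5%.

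**6. Unequal dropout, placebo −3 and caffeine −6 (assumed).**

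| Dropout, placebo / caffeine | Placebo mean | Caffeine mean | Difference |
|---|---|---|---|
| 10% / 30% | 0.9 × −3 = −2.7 | 0.7 × −6 = −4.2 | −1.5 |
| 30% / 10% | 0.7 × −3 = −2.1 | 0.9 × −6 = −5.4 | −3.3 |

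The true difference is −3. The first pattern halves it (power about 36%); the second overstates it.

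**7. Unequal dropout, no true effect, both arms −5 (assumed), 10% placebo and 30% caffeine.**

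- Means: −4.5 and −3.5, so the bias is +1.0, against caffeine.
- Variances: 0.9 × 50 − 20.25 = 24.75 and 0.7 × 50 − 12.25 = 22.75.
- SE = √(47.5 / 55) = 0.929, and the bias is 1.076 SEs.
- Rejections: 18.8% favouring placebo plus 0.1% favouring caffeine, about 19% in total.

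**The case against.** Several limits on this point are fair.

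- **Not every dropout is set to zero.** A reader might infer that from the rule, but the mITT definition removes anyone with no follow-up assessment. If that term meant a post-baseline Fibroscan, no zeros would arise for CAP or LSM. The plan does not say so, and monthly visits make the visit reading the natural one.
- **The synopsis lists a 3-month scan.** If it is done, patients lost after month 3 would carry a month-3 value. Those lost before it would still get zero.
- **FIB-4 is different.** Patients lost after month 3 have a month-3 blood result to carry forward.
- **The reach of the rule is partly inferred.** The sentence follows one on safety outcomes, and withdrawal by the investigator is not plainly loss to follow-up. Section 7.7 also lists criteria under which only dosing stops. But the rule refers to analysis in general and exempts no endpoint.
- **Bias is conditional.** With equal dropout and no effect there is none in the difference.
- **The interval is not too narrow for what it estimates.** The SE is right for the zero-imputed estimator. The loss of coverage in step 3 comes from the shifted estimate.
- **The 19% is not a rate of false claims for caffeine.** It rests on assumed inputs, and nearly all of those rejections favour placebo. The protocol gives no dropout rate by arm, and it excludes patients sensitive to caffeine or with arrhythmia, so higher dropout on caffeine is possible but not established.

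An SAP may exist and may hold imputation detail. That would not cure a rule that the protocol itself states.

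**Conclusion.** The rule is wrong as written for CAP and LSM. Under the schedule in sections 4.6 and 5.5 and Table 2, an analysed patient lost before month 6 is given a change of exactly zero.

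The firm part of the size is proportional: with equal dropout and unseen changes like those of completers, a true effect shrinks by the share imputed. That is at most 20% at the planned dropout, and about 11% if half of the dropouts enter the mITT set. At equal dropout the power loss is small when placebo change is zero (79.0% against 80.4%) and grows with the assumed placebo change.

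Dropout that differs by arm can bias the difference in either direction and raise type I error. The figures for that are illustrations, because the arm changes and unequal rates are assumed and the SD of 5 and difference of 3 carry no unit. The documents do not support saying that the primary effect is biased in all circumstances, or in a known direction.

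**What to change.** 1. In section 4.8, remove last-value carry-forward for CAP and LSM. Analyse month-6 CAP and LSM by assigned arm with ANCOVA adjusted for the baseline value. Handle missing scans by multiple imputation from baseline and interim data already collected, such as monthly weight and month-3 bloods. Add a sensitivity analysis for data missing not at random.
2. In section 7.7, state that a participant who stops tablets still has the already scheduled month-6 Fibroscan unless consent is withdrawn. This concerns data collection only and leaves the stopping criteria as they are.
3. Reconcile synopsis item 9 with sections 4.6 and 5.5 and Table 2 on whether a 3-month Fibroscan is done.

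The cost is protocol wording and modest extra analysis; no new visit or scan is needed, since the month-6 scan is already scheduled for everyone. Item 2 should be settled before participants start to leave, because a scan that was not taken cannot be recovered.
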